#### Safety Monitoring Plan:

Potential subjects will provide information regarding their drug use history and undergo an extensive physical and psychiatric health screening to determine their eligibility and the safety of their participation. Any individual with a past or current serious physical or mental health condition, other than drug use disorder, that, in the opinion of the study physician would be contraindicated for study participation, or who have metallic implants, fragments or pacemakers, will be excluded from research participation. Individuals who report a first-degree family history of cardiovascular disease that resulted in premature death or seizures will also be excluded from research participation. Female subjects must be using an effective form of birth control and test negative for pregnancy prior to each experimental session. Potential subjects who report regular use of any psychotropic medication, or illicit drug other than cannabis, will be excluded. All study subjects will be judged by the medical staff to be psychiatrically and physically healthy. Methods for monitoring adverse events (AEs) will include unobtrusive observations by medical and research staff, spontaneous report by the subjects, regular measurement of physiological indices, subjective-effects questionnaires, and performance on experimental tasks. Subjects will not receive study drug if they have any signs or symptoms that may contraindicate its administration (e.g., HR outside of predetermined range).

All AEs occurring during the course of the study will be collected, documented, and reported to the PI and the Study Physician following each occurrence. The occurrence of AEs will be assessed daily for the duration of participation and as needed in follow-up visits as appropriate. The PI and Study Physician will follow all AEs to the point of a satisfactory resolution. Subjects may be withdrawn from the study if the investigators determine it is the best decision in order to protect the safety of the subject. All AEs will be assessed to determine if they meet criteria for a serious adverse event (SAE).

Serious adverse events, as defined by the FDA, will be systematically evaluated daily for the duration of participation, and as needed in follow-up visits as appropriate. Any SAE, whether or not related to brain stimulation, drug administration, or neuroimaging will be reported to the IRB, NIDA and the FDA. In the event that a subject either withdraws from the study or the investigator decides to discontinue a subject due to an SAE, the subject will have appropriate follow-up medical monitoring. Monitoring will continue until the problem has resolved or stabilized with no further change expected, is clearly unrelated to the study drugs, or results in death. A summary of the SAEs that occurred during the previous year will be included in the annual progress report to NIDA.

[Back to Top](#)

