## Research Procedures

Describe how the research will be conducted.

- What experience will study participants have?
- What will study participants be expected to do?
- How long will the study last?
- Outline the schedule and timing of study procedures.
- Provide visit-by-visit listing of all procedures that will take place.
- Identify all procedures that will be carried out with each group of participants.
- Describe deception and debrief procedures if deception is involved.

Differentiate between procedures that involve standard/routine clinical care and those that will be performed specifically for this research project. List medications that are explicitly forbidden or permitted during study participation.

See Table 1 (attached) for a list of study visits and Figure 1b for a schematic of the procedures during experimental sessions. Excluding approximately two screening visits prior to study enrollment (carried out under our screening protocol IRB#: 43686), the study proper will consist of seven (7) outpatient visits: 1 training session (Visit 1) and 6 brain stimulation (TMS) and drug administration experimental sessions (Visits 2-7) taking place over approximately 3-5 weeks. Experimental sessions (Visits 2-7) will last for approximately 7 hours and will be separated by at least 48 hours.

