### Brain Stimulation and Drug Administration Experimental Sessions (Visits 2-7):

Experimental sessions during Experiments 1 and 2 will last approximately 7 hours and test 6 combinations of TMS and THC on relevant outcome measures (Visits 2-7; Figure 1). Subjects in Experiment 1 will receive real and sham excitatory iTBS of the left DLPFC. Subjects in Experiment 2 will receive real and sham inhibitory cTBS of the left DLPFC. A single bout of iTBS or cTBS (real or sham) TMS will be delivered at a single time point (approximately 3 hours after capsule administration) during each experimental session. Subjects will receive the 6 experimental conditions in random order except that the combination of 30 mg THC + active TMS condition (iTBS or cTBS) will not be administered prior to the administration of 30 mg THC + sham TMS.

Drug Administration: THC (10 and 30 mg) and placebo will be administered orally under double-blind conditions. The oral route was chosen to maintain subject and research staff blindness and to eliminate any expectations that may accompany other routes of drug administration (i.e., smoking). Subjects will ingest capsules with approximately 150 mL of water. Research staff will conduct a mouth check to ensure that the subject swallowed the capsules. Placebo will also be tested and capsules will be filled with a behaviorally inert substance (e.g., corn starch). If heart rate is above 100 bpm before dose administration, the dose will be withheld and heart rate reassessed every 15 minutes for 1 hour. If heart rate has not fallen below 100 bpm after 1 hour, the study physician will be consulted regarding the subject's continued participation in the study.

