The doses of THC will be 10 and 30 mg. Capsules will contain commercially available delta-9-THC (Marinol; dronabinol). This active dose was chosen based on our previous laboratory research with THC in humans (Lile et al., 2009, 2010a, 2010b, 2011, 2012a, 2012b, 2013, 2014, 2015). For comparison, the therapeutic dose range indicated for antiemesis is 5-20 mg administered 4-6 times per day. The starting therapeutic dose range indicated for appetite stimulation is 2.5-10 mg administered prior to lunch and dinner, but this can be increased up to 20 mg. We have previously administered up to 90 mg THC acutely (Lile et al., 2013) in individuals with less cannabis experience than proposed in the present study. Plasma concentrations for oral THC peak from 2-4 hours, which is consistent with the proposed experimental procedures (Hollister et al., 1981). The half-life of THC is 19-36 hours, but the duration of the psychoactive effects last only 4-6 hours (Hollister et al., 1981; Lemberger et al., 1972).

**TMS Coil Placement and Stimulation Parameters:** For real and sham sessions in both experiments, rMT will be determined before the delivery of iTBS (Exp. 1) and cTBS (Exp. 2) using standard single-pulse motor mapping procedures (described above) during each experimental session. Determination of rMT before delivery of TMS (i.e., iTBS or cTBS) during each session is necessary because rMT varies across individuals and in response to various environmental and individual factors (e.g., across days and times of day, amount of sleep) and ensures that the minimum necessary stimulation intensity is used during the TMS protocol during each experimental session. rMT will be determined after check-in procedures have been completed, prior to capsule administration.

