Common side effects of cannabinoid agonists such as cannabis and THC include anxiety, asthenia, ataxia, myalgia, akathisia, tachycardia, palpitations, arrhythmias, hypotension, flushing, abdominal pain, nausea, vomiting, diarrhea, constipation, dry mouth, headache, change in appetite, cognitive and mood disturbances (e.g., euphoria, paranoia, depersonalization, amnesia, confusion and memory impairment), sleep disturbances and nightmares, speech difficulty, dizziness, sedation, somnolence, hypothermia and shortness of breath. It is likely that subjects will experience one or more of these side effects. In addition, these drugs may exacerbate psychiatric symptoms in individuals with certain mental health disorders (i.e., mania, depression or schizophrenia). Unsupervised self-administration of higher doses of cannabis has resulted in more serious side effects such as psychotic episodes and panic attacks. It is unlikely that subjects will experience these more serious side effects. In addition, seizures can occur in subjects with existing seizure disorders. The occurrence of seizures appears to be related to the presence of certain predisposing factors including histories of head trauma, CNS tumors and previous incidence of seizures. Individuals reporting any of these predisposing factors will be excluded from participation, so the risk of seizure is extremely low. In addition, cannabis interacts with other licit and illicit drugs and alcohol. All subjects will be monitored for use of unauthorized drugs throughout the study and will be appropriately cautioned about their activities before and after their participation, so the risk of interactions with other drugs is also low.

6. Side effects associated with brain stimulation.

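### Adverse events are to be assessed daily, but only seven visits and no scheduled contact after Visit 7 are described, so active follow-up of the last session is uneven across conditions

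*Combined protocol and SAP*

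**What the plan says.** The Safety Monitoring Plan sets the frequency of AE assessment: "The occurrence of AEs will be assessed daily for the duration of participation and as needed in follow-up visits as appropriate". Serious adverse events "will be systematically evaluated daily for the duration of participation, and as needed in follow-up visits as appropriate". The listed methods are staff observation, spontaneous report, physiological measures, subjective-effects questionnaires and task performance. The section also undertakes to collect every AE that arises during the study and to follow it until resolved.

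Research Procedures says that "the study proper will consist of seven (7) outpatient visits", one for training and six experimental, "taking place over approximately 3-5 weeks". Experimental sessions "will be separated by at least 48 hours". The Payment section allows for extra visits but places them among the experimental sessions. The protocol describes no diary, call or survey on non-visit days, and no scheduled visit or call after Visit 7.

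The section on the experimental sessions (Visits 2-7) makes the order of the six conditions random with one restriction: the "30 mg THC + active TMS condition (iTBS or cTBS) will not be administered prior to the administration of 30 mg THC" with sham stimulation.

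**The concern.** The stated frequency does not fit the schedule. If subjects attend on seven days and no other contact is arranged, nobody is assessing them daily.

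The more important part is what happens to events that start after discharge. Potential Risks & Benefits lists "sleep disturbances and nightmares" among the common side effects of cannabinoids, and such events would mostly occur at home. After Visits 2 to 6 the subject can mention them at the next check-in, although the listed check-in steps include no question about events since the previous session. After Visit 7 there is no next check-in. Even a literal daily assessment for the duration of participation would leave this session without follow-up if participation ends at Visit 7.

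The order restriction influences which condition comes last, so the gap is not shared evenly. At stake are the fairness of any AE tabulation by condition and the chance that a late event after the final session reaches the investigator or study physician.

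**Working it through.** The plan gives no figure on this point to reproduce, so the check is a count of admissible orders plus simple coverage arithmetic.

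**Coverage.** Inputs from Research Procedures: 7 visits in 3-5 weeks, that is 21-35 days. 7/21 = 33% and 7/35 = 20%. At least two thirds of the days have no described contact.

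**Which condition is last.** Six conditions (real or sham TMS with 0, 10 or 30 mg THC), with 30 mg + sham before 30 mg + real.

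- All orders: 6! = 720. Half satisfy the restriction: 720/2 = 360.
- 30 mg + real last: the other five can take any order, 5! = 120, so 120/360 = 1/3.
- 30 mg + sham last: 0/360.
- Each of the other four last: 5!/2 = 60, so 60/360 = 1/6.
- Sum: 1/3 + 0 + 4 × 1/6 = 1.

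With the 40 subjects given under Data and Safety Monitoring, all completing: 40/3 = 13.3 for 30 mg + real, 0 for 30 mg + sham, and 40/6 = 6.7 for each other condition. With the form's maximum of 80: 26.7, 0 and 13.3.

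**Sensitivity to how the order is drawn.** If conditions are drawn one at a time from those still allowed, 30 mg + real is last in 137/300 = 45.7%, 30 mg + sham in 0, and each other condition in 163/1200 = 13.6%.

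**Sensitivity to dropout.** The protocol gives no dropout rate. The range below is assumed, with an equal chance of stopping after each of sessions 1 to 5.

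| Assumed total dropout | Last session received is 30 mg + real | Last session received is 30 mg + sham |
|---|---|---|
| 10% | 31.3% | 2.0% |
| 20% | 29.2% | 4.1% |
| 30% | 27.1% | 6.3% |

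**Effect on recorded AEs.** Let p be the true rate of delayed AEs per session, equal in both 30 mg conditions. Let a be the probability that such an event is recorded when a visit follows, and b the probability when none does. Among completers:

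- 30 mg + sham: p × a
- 30 mg + real: p × (2/3 × a + 1/3 × b)
- Difference: p × (a − b)/3

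The difference is in favour of real TMS whenever a exceeds b, and zero if they are equal. None of p, a and b is given, so no number can be put on it. The relative loss for 30 mg + real cannot exceed 1/3, reached only if b = 0.

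**The case against.** The strongest case against the point is that the plan does not leave subjects without contact. Records, Privacy, and Confidentiality says that subjects have telephone details for the investigator and study physician, that both (or the physician's representative) can be reached at all times, and that protocol management forms prompt staff to record unusual events. The Safety Monitoring Plan lists spontaneous report and allows as-needed follow-up visits. A reader might infer that delayed events after Visit 7 go uncollected. The documents do not support that: such events are not actively sought, but they can still be reported.

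Four other stronger readings also fail.

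- A reader might infer that 30 mg + sham never lacks a later visit. That is exact only for completers; under the assumed dropout it is the last session for 2-6% of subjects.
- A reader might set the session's end against the statement "The half-life of THC is 19-36 hours". The capsule comes about 1.5 hours into a session of about 7 hours, so the planned end is about 5.5 hours after dosing. But the same sentence puts the psychoactive effects at 4-6 hours, and the section on effects of the study drugs keeps subjects on site while drug effects persist. The half-life does not show that subjects leave while affected, and the point does not need it.
- A reader might infer a biased trial result. No real-versus-sham AE comparison is planned; the ANOVAs concern task and other study outcomes, and the monitoring report summarises serious events.
- A reader might take daily assessment to be impossible by design. The word may be meant as each session day, though the text does not say so.

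Table 1, Figure 1 and the separate screening protocol are not available here and could mention a further contact. Research Procedures nevertheless counts seven visits in all.

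These points limit the claim. Telephone access and as-needed visits depend on the subject coming forward, and following AEs to resolution applies only to events already known. No described provision is a scheduled enquiry after the last session.

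**Conclusion.** The point holds as a defect in safety ascertainment. The assessment frequency stated for AEs and SAEs does not match the described visits, and active enquiry after the final session is unspecified. Among completers that final session is 30 mg + real in 1/3, 30 mg + sham in none, and each other condition in 1/6. This assumes that all 360 admissible orders are equally likely and that no scheduled contact exists beyond those described. The ranking of the two 30 mg conditions survives both sensitivity checks.

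A descriptive AE summary at 30 mg would tend to favour real TMS, provided that a following visit makes a report more likely. How much is unknown, because neither a delayed-AE rate nor a reporting probability is given. The primary efficacy analyses are not touched.

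**What to change.** Two changes to the Safety Monitoring Plan:

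1. Reword the frequency for AEs and SAEs so that it matches the schedule, that is, assessment on each session day.
2. Add one structured AE query at the same fixed interval after every experimental session, including Visit 7 or, for a subject who stops early, the last session received. A short REDCap survey or a call would do, no later than the 48-hour minimum gap and before the next dosing. Attribute each reported event to the condition of the preceding session.

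Among completers this reduces the share of sessions without a scheduled enquiry from 1/3, 0 and 1/6 to 0 in all six conditions. The study already uses REDCap, so the cost is a short amendment and one brief contact per session. The downside is a small added burden and some non-response after the last session, which should be reported by condition.

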#### Future Use and Sharing of Material (e.g., Data/Specimens/Information)

If the material collected for this study will be used by members of the research team or shared with other researchers for future studies, please address the following:

- list the biological specimens and/or information that will be kept
- briefly describe the types, categories and/or purposes of the future research
- describe any risks of the additional use
- describe privacy/confidentiality protections that will be put into place
- describe the period of time specimens/information may be used
- describe procedures for sharing specimens/information with secondary researchers
- describe the process for, and limitations to, withdrawal of specimens/data

De-identified information will be securely stored at the University of Kentucky NSL indefinitely. De-identified data may be used for future research or shared with other researchers. Those data may include demographic, physical, mental health, medical history, and/or drug use history information that can be used to describe the study population and facilitate experimental analyses of neurobehavioral outcomes related to the study population. There is a risk that someone could get access to the information in spite of the security measures and safeguards. There may also be risks that at this time are unknown. A researcher from another institution may request to receive de-identified information by contacting the study PI, that request will also be reviewed by the IRB. Information will not be shared with researchers in other countries.

Are you recruiting or expect to enroll **Non-English Speaking Subjects or Subjects from a Foreign Culture?** (does not include short form use for incidentally encountered non-English subjects)

Yes  No

Non-English Speaking Subjects or Subjects from a Foreign Culture

#### Recruitment and Consent:

Describe how information about the study will be communicated to potential subjects appropriate for their culture, and if necessary, how new information about the research may be relayed to subjects during the study.

When recruiting Non-English-speaking subjects, provide a consent document in the subject's primary language. After saving this section, attach both the English and translated consent documents in the "Informed Consent" section.

**Cultural and Language Consultants:**

The PI is required to identify someone who is willing to serve as the cultural consultant to the IRB.

- This person should be familiar with the culture of the subject population and/or be able to verify that translated documents are the equivalent of the English version of documents submitted.
- The consultant should not be involved with the study or have any interest in its IRB approval.
- Please include the name, address, telephone number, and email of the person who agrees to be the cultural consultant for your study.
- ORI staff will facilitate the review process with your consultant. Please do not ask them to review your protocol separately.

For more details, see the IRB Application Instructions on [Research Involving Non-English Speaking Subjects or Subjects from a Foreign Culture](#).

**Local Requirements:**

If you will conduct research at an international location, identify and describe:

- relevant local regulations
- data privacy regulations
- applicable laws
- ethics review requirements for human subject protection

Please provide links or sources where possible. If the project has been or will be reviewed by a local ethics review board, attach a copy in the "Additional Information/Materials" section. You may also consult the current edition of the [International Compilation of Human Research Standards](#)
